12.8.3 Completing the MRI + 1 Month Visit

1. The PG data must be reviewed to document whether any new episodes of polymorphic or monomorphic VT or VF that required ATP or shock therapy are present, following the MRI visit.
 - a. If polymorphic or monomorphic VT or VF episodes are present:
 - i. Print the ‘Arrhythmia Logbook’ and ‘Selected Episodes Report’ (counters and EGMs) using the PRM
 - ii. A copy of the Selected Episode Report(s) with counters and EGMs is expected to be submitted to Boston Scientific **within 5 business days** using the upload tool in the EDC system
 - iii. If a physical copy of the Selected Episode Report(s) is to be submitted (instead of an electronic upload), the copy is expected to be submitted to the ECG Core Lab **within 5 business days**
2. Program the device according to physician discretion, and indicate if any permanent device programming was changed
3. Print the ‘Quick Notes’ Report
4. Perform a Save All:
 - a. Save device data to a USB using the programmer “Save All” feature
 - b. Label the USB with the subject ID#, Date, and “MRI + 1 month”
 - c. Retain the original USB at the center, a copy is expected to be submitted to Boston Scientific **within 5 business days** using the upload tool in the EDC system
 - i. If a physical copy of the USB is to be submitted (instead of an electronic upload) use a PC to make the copy and label it the same way as the

original. **Do not make a copy by using the programmer a second time as this will create a new USB with slightly different information.**

5. Schedule the Annual follow-up visit.

12.8.4 MRI + 1 Month Visit Source Data Requirements

Source data requirements at MRI+1 month Visit are described in Table 12-7:

Table 12-7: MRI + 1 Month Source Documentation Requirements

Source Documentation Requirement	Disposition
Device Evaluation (pace threshold, sense amplitude, impedance, RV shock impedance, LV Phrenic Stimulation threshold)	Retain at center
PRM ECG strips from manual threshold tests documenting LOC for all implanted leads	
VF Induction real-time ECG and electrogram strips, if VF induction occurred	
Printout of 'Quick Notes' Report and 'Devices Settings Report' showing the VF induction settings, if VF induction occurred	
Documentation of spontaneous VT/VF episode(s) by PRM strips, as applicable: 
 • 'Selected Episodes Report' (counters and EGMs required) • 'Arrhythmia Logbook' 	
Printout of Final 'Quick Notes' Report	
Adverse Events	Retain the original at the center and submit a copy to Boston Scientific
Save All	

12.9 Every Three-month Follow ups through Three Years (Recommended)

For Phase I and Phase II patients with a MR scan (study required MR scan or medically necessary MR scan):

- If the patient is followed on LATITUDE NXT, monitoring of device performance is strongly recommended at least every 3 months
- If the patient is not followed on LATITUDE NXT, **an in-clinic follow-up schedule of every three months is strongly recommended to monitor device performance**

Timing for each follow up is:

- First 3-month Follow-up: 90±30 days from MRI visit

- Second 3-month Follow-up: 180±30 days from MRI visit
- Third 3-month Follow-up: 270±30 days, and so on

12.9.1 Device Evaluation

1. The standard of care evaluation for device performance is recommended. Record the available measurements in the EDC system.
 - Pacing thresholds (if LATITUDE NXT is used, collect thresholds if available)
 - Sensing amplitude
 - Impedance
 - Shock impedance (RV lead only)
2. If any new episodes of polymorphic or monomorphic VT or VF that required ATP or shock therapy are present since the prior study visit:
 - i. Print the ‘Arrhythmia Logbook’ and ‘Selected Episodes Report’ (counters and EGMs)
 - ii. A copy of the Selected Episode Report(s) with counters and EGMs is expected to be submitted to Boston Scientific **within 5 business days** using the upload tool in the EDC system
 - iii. If a physical copy of the Selected Episode Report(s) is expected to be submitted (instead of an electronic upload), the copy must be submitted to the ECG Core Lab **within 5 business days**
3. Program the device according to physician discretion, if applicable
4. Print the ‘Quick Notes’ Report

12.9.2 Every Three-month Visit Source Data Requirements

Source data requirements at Every Three-month visits are described in Table 12-8.

Table 12-8: Every Three Month Source Documentation Requirements

Source Documentation Requirement	Disposition
Document if polymorphic or monomorphic VT/VF episodes requiring therapy, are present Documentation of VT/VF episode(s) by PRM strips, as applicable: 
 • ‘Selected Episodes Report’ (counters and EGMs required) • ‘Arrhythmia Logbook’ 	Retain at center
Printout of ‘Quick Notes’ Report	
Adverse Events	

12.10 Annual Follow ups through Three Years

For de novo: Annual follow-ups must be performed as an in-clinic visit, starting at one year post implant and continuing until 3 years post implant.

For existing implants: Annual follow-ups must be performed as a clinic visit, starting at one year post enrollment and continuing until 3 years post enrollment.

Timing for each follow up is:

- 1 Year Follow-up: 365±90 days
- 2 Year Follow-up: 730±90 days
- 3 Year Follow-up: 1095±90 days

12.10.1 Standard Device Evaluation

All implanted leads will be evaluated through the implanted PG for:

- Manual pacing threshold tests (testing parameters per physician discretion)
- Sensing amplitude
- Impedance
- Shock impedance (RV lead only)

Record the measurements in the EDC system.

12.10.2 Completing the Annual Visit

1. For all annual visits after an MR scan, the PG data must be reviewed to document whether any new episodes of polymorphic or monomorphic VT or VF that required ATP or shock therapy are present since the prior study visit.
 - a. If polymorphic or monomorphic VT or VF episodes are present:
 - i. Print the 'Arrhythmia Logbook' and 'Selected Episodes Report' (counters and EGMs) using the PRM
 - ii. A copy of the Selected Episode Report(s) with counters and EGMs is expected to be submitted to Boston Scientific **within 5 business days** using the upload tool in the EDC system
 - iii. If a physical copy of the Selected Episode Report(s) is to be submitted (instead of an electronic upload), the copy is expected to be submitted to the ECG Core Lab **within 5 business days**

2. Program the device according to physician discretion
3. Print the 'Quick Notes' Report
4. Perform a Save All:
 - a. Save device data to a USB using the programmer "Save All" feature
 - b. Label the USB with the subject ID#, Date, and "Annual"
 - c. Retain the original USB at the center, and a copy is expected to be submitted to Boston Scientific **within 5 business days** using the upload tool in the EDC system
 - i. If a physical copy of the USB is to be submitted (instead of an electronic upload) use a PC to make the copy and label it the same way as the original. **Do not make a copy by using the programmer a second time as this will create a new USB with slightly different information.**
5. Schedule the next annual follow-up visit.

12.10.3 Annual Visit Source Data Requirements

Source data requirements at annual visits are described in Table 12-9.

Table 12-9: Annual Source Documentation Requirements

Source Documentation Requirement	Disposition
Device Evaluation (pace threshold, sense amplitude, impedance, RV shock impedance)	Retain at center
PRM ECG strips from manual threshold tests documenting LOC for all implanted leads	
Document if polymorphic or monomorphic VT/VF episodes requiring therapy, are present Documentation of VT/VF episode(s) by PRM strips, as applicable: 
 • 'Selected Episodes Report' (counters and EGMs required) • 'Arrhythmia Logbook' 	
Printout of 'Quick Notes' Report	
Adverse Events	
Save All	Retain the original at the center and submit a copy to Boston Scientific

12.11 Additional Visits

An Additional Follow-up Visit will be reported when an office/clinic visit identifies a reportable event and the device is interrogated (see Section 22.1). If possible, a device evaluation and lead measurements should be performed and the results recorded in the EDC system.

12.11.1 Required Data Collection

1. Complete the Additional Follow-up form
2. Collect any adverse event information
3. Print the 'Quick Notes' Report

12.11.2 Recommended Data Collection

1. It is recommended to conduct a device evaluation:
 - Manual pacing threshold tests
 - Sensing amplitude
 - Impedance
 - Shock impedance (RV lead only)
2. For all additional visits after an MR scan, the PG data should be reviewed to document whether any new episodes of polymorphic or monomorphic VT or VF that required ATP or shock therapy are present since the prior study visit.
 - a. If polymorphic or monomorphic VT or VF episodes are present:
 - i. Print the 'Arrhythmia Logbook' and 'Selected Episodes Report' (counters and EGMs) using the PRM
 - ii. A copy of the Selected Episode Report(s) with counters and EGMs is expected to be submitted to Boston Scientific **within 5 business days** using the upload tool in the EDC system
 - iii. If a physical copy of the Selected Episode Report(s) is to be submitted (instead of an electronic upload), the copy is expected to be submitted to the ECG Core Lab **within 5 business days**
3. Perform a Save All:
 - a. Save device data to a USB using the programmer "Save All" feature
 - b. Label the USB with the subject ID#, Date, and "Additional Follow-up"
 - c. Retain the original USB at the center, and a copy is expected to be submitted to Boston Scientific **within 5 business days** using the upload tool in the EDC system
 - i. If a physical copy of the USB is to be submitted (instead of an electronic upload) use a PC to make the copy and label it the same way as the original. **Do not make a copy by using the programmer a second time as this will create a new USB with slightly different information.**

Record the measurements in the EDC system for any tests performed.

12.11.3 Additional Follow-up Visit Source Data Requirements

Source data Requirements at Additional Follow-up Visit are described in Table 12-10.

Table 12-10: Additional Follow-up Source Documentation Requirements

Source Documentation Requirements	Disposition
Device Evaluation (pace threshold, sense amplitude, impedance, RV shock impedance), as applicable	Retain at center
PRM ECG strips from manual threshold tests documenting LOC for all implanted leads	
Document if polymorphic or monomorphic VT/VF episodes requiring therapy, are present Documentation of VT/VF episode(s) by PRM strips, as applicable: 
 • 'Selected Episodes Report' (counters and EGMs required) • 'Arrhythmia Logbook' 	
Printout of 'Quick Notes' Report	
Adverse Events	
Save All, as applicable	Retain the original at the center and submit a copy to Boston Scientific

Text in table that is italicized is recommended

12.12 Medically Necessary MRI Visits

During the study, if a subject needs a medically necessary MR scan, BSC recommends the subject be directed to have the scan at the Study site.

Note: In case the medically necessary MR scan is performed at a non-investigational site, all efforts must be made to collect the data and adhere to the MRI Conditions of Use.

Study flow is identical to the MRI visit as described in section 12.7. Some data collection is optional for Medically Necessary MRI visit as shown in italic in Table 12-11.

For medically necessary MRI scans, all activities performed by the site Principal Investigator or a sub-investigator at the MRI visit (i.e. heart rhythm monitoring, hemodynamic monitoring) can be performed by a trained and qualified Health Care Professional (HCP).

As for the MRI visit, it is recommended to have a programmer powered ON in Zone II near the MRI room in case the patient develops the urgent need for pacing.

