11.1 Screening and Point of Enrollment

11.1.1 Subjects enrolled under previous protocol versions

All subjects enrolled under previous protocol versions will need to be re-consented. The exclusion criterion #5 will need to be evaluated for these patients:

- Subjects not having performed the MRI visit:
 - If these subjects meet the updated exclusion criterion #5, they should be withdrawn from the study and classified as consent ineligible subjects. These withdrawn subjects will not count against the enrollment ceiling.
 - If these subjects do not meet the updated exclusion criterion #5:
 - They will continue as part of Phase I and will undergo the non-diagnostic study required MR scan
 - If they refuse to undergo the non-diagnostic study required MR scan (Phase I), they will automatically be rolled onto Phase II unless they

chose to withdraw from the study. These withdrawn subjects will not count against the enrollment ceiling.

- Subjects having performed the MRI visit:
 - If these subjects do not meet the updated exclusion criterion #5, they will continue in the study and attend visits as required per protocol. These subjects are counting toward the enrollment ceiling.
 - If these subjects meet the updated exclusion criterion #5, this should be documented in the subject’s file. These subjects can remain enrolled in the study. In case of withdrawal, if possible, such subjects should not be withdrawn prior to the MRI + 1 month to ensure safety follow-up within 30 days post MRI. These subjects are counting toward the enrollment ceiling.

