11.2 Withdrawal

All subjects enrolled in the clinical study (including those withdrawn from the clinical study or lost to follow-up) shall be accounted for and documented. If a subject withdraws from the clinical investigation, the reason(s) shall be reported.

For US subjects: If such withdrawal is due to problems related to investigational device safety or performance, the investigator shall ask for the subject’s permission to follow his/her status/condition outside of the clinical study until the implanted investigational devices are approved by the FDA or the device is explanted.

Reasons for withdrawal include, but are not limited to:

- Subject who does not receive a Boston Scientific ImageReady MR Conditional Defibrillation System (no follow-up requirements)
- Subject who receive only a partial Boston Scientific ImageReady MR Conditional Defibrillation System (see section 11.3.4 for follow-up requirements)
- Subjects that have a PG or lead changeout that is not a Boston Scientific ImageReady MR Conditional Defibrillation System component (See Section 5)
- Subjects in Phase I who refuse to undergo the study require MR scan and are not willing to be rolled into Phase II
- Subjects already enrolled with previous protocol versions, who have not performed the MRI visit and who meet the updated exclusion criterion #5
- Subjects who fail the heart rhythm monitoring requirements at the MRI visit
- Physician discretion
- Subject choice to withdraw consent
- Lost to follow-up
- Death

While study withdrawal is discouraged, subjects may withdraw from the ENABLE MRI study and/or the VF Induction Sub-study at any time, with or without reason, and without prejudice to further treatment.

All applicable case report forms up to the point of subject withdrawal and a “Subject Status” form must be completed. Subjects who are “lost-to-follow-up” should have documented attempts to contact them prior to completion of the “Subject Status” form.

Additional study data may no longer be collected after the point at which a subject has been withdrawn from the study or withdraws his/her consent, for whatever reason. All open adverse events should be closed or documented as chronic. Data collected up to the point of subject withdrawal may be used.

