12.7.2.2 Subject History of Unexplained Syncope

Prior to the MR Scan, subjects should be questioned or a current medical history review should occur to determine if there is any history of unexplained syncope (loss of consciousness). If confirmed, the subject should not proceed with the study-required MR scan and be withdrawn from the study.

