12.7.2.3 Heart Rhythm Monitoring prior to MRI protection mode programming

It is **required** that the heart rhythm be monitored by the site Principal Investigator or a sub-investigator for all subjects prior to initiation of the MRI Protection Mode and the MR Scan.

- Monitoring is to be performed in VVI 40 programming
- Monitor the heart rhythm using the programmer EGRAMs for at least 5 minutes. Heart rate and any abnormal rhythms, including incidence of ectopy shall be documented.
 - In particular, look for signs of progressive AV nodal block over time, permanent or intermittent complete AV block, or trifascicular block (alternating bundle branch block or PR > 200 ms with LBBB or other bifascicular block) or a paced event (one single paced beat) during this time period. **Any** occurrence of these events will disqualify subjects from undergoing the MRI.
 - Such subjects should be withdrawn from the study.
 - Required ECG documentation
 - 12 lead ECG and a 10s rhythm strip to be printed at any time during the 5 minutes of the monitoring (either from the ECG machine or the BSC PRM)
 - Any abnormal rhythms / ectopy shall be documented with a printed ECG or rhythm strip if possible.

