12.7.3.2 Heart Rhythm Monitoring after MRI protection mode programming

It is **required** that the heart rhythm be monitored by the site Principal Investigator or a sub-investigator for all subjects after programming MRI protection mode ON and prior to initiation of the MR Scan.

- Monitor the heart rhythm for at least 5 minutes using the monitoring equipment screen. Heart rate and any abnormal rhythms, including incidence of ectopy shall be documented.
 - In particular, look for signs of progressive AV nodal block over time, permanent or intermittent complete AV block, or trifascicular block (alternating bundle branch block or PR > 200 ms with LBBB or other bifascicular block) or a sinus pause > 2s during this time period. **Any** occurrence of these events will disqualify subjects from undergoing the MRI.
 - For such subjects, MRI protection mode must be turned OFF. These subjects should be withdrawn from the study.

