13.2.4 Assessment of VT/VF

In Phase I, VT and VF episodes from the following three sources will be collected and analyzed:

- Spontaneous VT/VF episodes that required therapy
- VT/VF episodes from “for-cause” VF induction
- VF Induction Sub-study VT and VF episodes

The VT/VF episodes will be evaluated by an ECG Core Lab. The performance objective is to demonstrate the continued ability of the ImageReady MR Conditional Defibrillation System to sense and detect VF post-MR scan (Phase I). Any instances of a detection delay of ≥ 5 seconds above the detection time expected, based on the VF rate and programming, will be further evaluated and the analysis will be provided.

In addition, Boston Scientific plans to collect available spontaneous VT/VF episodes post MR scan from Phase I and II subjects over a 3-year follow-up period. The VT/VF episodes will be evaluated by an ECG core lab. A summary of the results from the ECG core lab will be included in the study report.

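### Section 12.12 does not say whether failing a pre-scan check at a medically necessary MRI visit ends enrollment; read as written, the imported rhythm rules would withdraw subjects already scanned

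*Combined protocol and SAP*

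**What the plan says.** Section 12.12 imports the procedure for medically necessary MRI visits from the Phase I MRI visit: "Study flow is identical to the MRI visit as described in section 12.7". It states two relaxations. One concerns data: "Some data collection is optional for Medically Necessary MRI visit as shown in italic in Table 12-11". The other lets a trained health care professional do the monitoring that an investigator must do at the study scan. Neither mentions enrollment.

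The imported section attaches withdrawal to three checks:

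- Unexplained syncope (12.7.2.2): if confirmed, "the subject should not proceed with the study-required MR scan and be withdrawn from the study".
- Rhythm monitoring before MRI Protection Mode (12.7.2.3): AV block, trifascicular block or a single paced beat at VVI 40 rules out the MRI, and "Such subjects should be withdrawn from the study".
- Rhythm monitoring after MRI Protection Mode is on (12.7.3.2): the same conduction findings, or a sinus pause over 2 s, rule out the MRI, and "These subjects should be withdrawn from the study".

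Section 11.2 gives the consequence: "Additional study data may no longer be collected after the point at which a subject has been withdrawn from the study". Its list of withdrawal reasons, which it says is not exhaustive, includes failing the rhythm requirements at the MRI visit.

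For subjects from earlier protocol versions who have already had the MRI visit and now meet exclusion criterion #5, section 11.1.1 says "this should be documented in the subject’s file. These subjects can remain enrolled in the study".

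Section 13.2.4 plans to "collect available spontaneous VT/VF episodes post MR scan from Phase I and II subjects over a 3-year follow-up period". Section 13.2.5 plans three years of data on medically necessary scans, with separate summaries for subjects scanned more than once.

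**The concern.** Withdrawal makes sense for a Phase I subject who cannot have the study scan. A subject already scanned is in a different position, because the remaining reason to keep that person enrolled is the post-scan record. If a failed check before a later clinical MRI ends enrollment, the study loses the annual visits, the post-scan VT/VF review and adverse event reporting for that person.

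The loss would not be random. It would fall on scanned subjects who show AV block, a pause, a need for pacing or, on one reading, unexplained syncope. Section 20.4 lists bradycardia, syncope and arrhythmia induction among the possible harms of scanning, so the exit rule overlaps with findings that the long-term follow-up should be able to describe.

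There is also an operational risk. Sites facing the same finding could act differently, because the protocol does not state the consequence for this visit.

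**Working it through.** The protocol gives no figure to reproduce here. The check is a comparison of passages, followed by simple arithmetic on follow-up time.

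**1. Do the checks apply at a medically necessary MRI visit?** Yes. Table 12-1 requires the pre-MRI ECG and rhythm monitoring in the medically necessary MRI column. Table 12-11 lists the syncope assessment and the ECG without the italics that mark recommended items. Section 12.12 itself names heart rhythm monitoring among the activities to be done.

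**2. What follows from failing them?** The two rhythm sections refer to the MRI in general, and then to withdrawal from the study. No visible passage says that failure cancels only that scan. The syncope sentence is narrower: it names the study-required scan and concerns unexplained syncope only.

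**3. Which passages point the other way?** Section 11.2 ties the rhythm reason to the MRI visit, and Table 12-1 keeps that visit in a separate column from the medically necessary MRI. Section 11.1.1 lets already scanned legacy subjects who meet criterion #5 stay enrolled, and asks that any withdrawal, if possible, not precede MRI + 1 month. All the triggers in 12.7.3.2 appear in criterion #5. So do those in 12.7.2.3, except the single paced beat.

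**4. What does one withdrawal cost?** The inputs are the three-year follow-up (12.13) and, for de novo subjects, annual visits at days 365, 730 and 1095 after implant, each ± 90 (12.10).

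- Exit at month 6: 36 − 6 = 30 months lost. Month 6 is about day 183 (365 ÷ 2), before the first window opens (365 − 90 = day 275), so all three annual visits are lost.
- Exit at month 18: 36 − 18 = 18 months lost. Month 18 is about day 548 (1.5 × 365), after the year-1 window closes (365 + 90 = day 455) and before the year-2 window opens (730 − 90 = day 640), so two annual visits are lost.

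The annual visits matter because review of device data for VT/VF is mandatory there (12.10.2), whereas the three-month visits are only recommended (12.9).

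**5. How many subjects?** The documents do not say. They give neither the rate of medically necessary scans nor the share failing a check. As an assumption only, if 5–15% of scanned subjects come for such a scan and 5–10% of those fail, the affected share is 0.05 × 0.05 = 0.25% to 0.15 × 0.10 = 1.5%.

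**6. Effect on the episode count.** Section 13.3 sets the total at up to 500 subjects in order to observe 30 spontaneous post-scan VT/VF episodes. Assume that a fraction f of subjects leaves halfway through follow-up on average, with constant and equal episode rates. The expected count is then 30 × (1 − f/2): about 29.9 at f = 1%, 29.3 at f = 5% and 28.5 at f = 10%. The count barely moves. What remains is the selection of who leaves.

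**The case against.** The strongest reply is that withdrawal was never meant to carry over. The cross-reference cannot be fully literal: 12.7 is headed as Phase I only, requires the Section 28 scan sequences, and ends by scheduling the MRI + 1 month visit. None of that fits a clinical scan of any body part in a Phase II subject. On this view, flow means the order of procedures around the scan, and 11.2 confirms that withdrawal belongs to the study scan. This is a fair reading. It shows that the text is ambiguous; it does not settle the matter, because the 11.2 list is open-ended and the rhythm sections are worded generally.

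Other parts of the reply also stand. The affected assessments are ancillary and unpowered (13.2), and they use whatever data are available. Data up to withdrawal may be used, and the finding that triggers withdrawal can already be on record as an event. The rhythm triggers are conduction or bradycardia findings, not failures to sense VF. Section 11.1.2, which covers subjects enrolled under the current version, is redacted, as is most of 9.1 and 11.4, so a retention rule there cannot be excluded.

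The provision in 11.2 for following US subjects outside the study does not answer the point. It applies when withdrawal stems from the safety or performance of an investigational device, and it does not restore study data.

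**Conclusion.** The passages conflict and should be reconciled. On the visible text, the rhythm limb supports withdrawal of an already scanned subject at a medically necessary MRI visit. The syncope limb is doubtful, and 11.2 and 11.1.1 point towards retention. If sites follow the withdrawal reading, the result is a small but selective loss from the long-term ancillary assessments. The primary endpoints end at MRI + 1 Month and are largely unaffected.

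A reader might infer more than the documents support:

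- That the protocol plainly removes any scanned subject with new syncope. The rule concerns unexplained syncope and is worded for the study-required scan.
- That 11.1.1 states the opposite rule for the same findings. It is permissive, covers legacy subjects only, rests on criterion #5 (which omits a single paced beat), and does not promise three years of retention.
- That the long-term record is shown to look cleaner. The triggering event can stay on record; what would be lost is the later device and event history.
- That 0.25–1.5% is an estimate. It rests on assumed inputs, and the documents allow no estimate of the number affected.

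**What to change.** Reconcile 12.12, 12.7.2.2, 12.7.2.3, 12.7.3.2 and 11.2 by separating eligibility for a scan from retention in the study. State in 12.12 and in 11.2 that, for a subject who has already had a study-required or medically necessary scan, failing a pre-scan check at a medically necessary MRI visit does not by itself end enrollment. Annual visits, VT/VF review and adverse event reporting then continue.

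Leave all instructions on whether to scan as they are. In 12.7.2.2 the scan instruction and the withdrawal instruction share one sentence, so split it and qualify only the withdrawal part. Restricting the whole sentence to unscanned subjects would also narrow the scan instruction. Check the result against the redacted text of 11.1.2.

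The cost is a few sentences in an amendment and a few more annual visits in subjects already enrolled for three years.
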